# Recommended algorithm for physician directed analgesia (PDA) arm:

- o IV Hydromorphone 0.4 mg Q4H PRN for pain 4-6
- o IV hydromorphone 0.6 mg Q2H PRN for pain 7-10
- Rescue IV hydromorphone 0.4 mg Q2H PRN for pain 4-10 = only to be given as a 'rescue dose' if patient has persistent pain despite using Q4H PRN IV hydromorphone (breakthrough pain)
- o Maximum opioid dosing: 1 mg per hour and 3 mg of IV hydromorphone per 4 hours
- If patient has received more than 2 rescue doses for breakthrough pain in 12 hours or is in uncontrolled pain: Hospitalist's recommended step-up orders: IV hydromorphone 0.8 mg Q4H PRN 4-6

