## Recommended algorithm for patient controlled analgesia (PCA) arm:

- IV Hydromorphone 0.1 mg Q10 minutes
- Rescue IV hydromorphone 0.4 mg Q2H PRN for pain 4-6, hydromorphone 0.6 mg Q2H PRN for pain 7-10 = only to be given as a 'rescue' dose for if patient has persistent pain despite using PCA (breakthrough pain)
- Maximum opioid dosing: 1 mg per hour and 3 mg of IV hydromorphone per 4 hours
- If patient has received more than 2 rescue doses for breakthrough pain in 12 hours or is in uncontrolled pain: Hospitalist's recommended step-up orders: IV hydromorphone 0.2 mg Q10 minutes

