after transition to PO opioids. The modality of IV opioid administration will revert to the assigned treatment arm.

- Other aspects of each patient's routine clinical care will continue as per the attending physician under whom the patient is admitted regardless of treatment arm status (PDA vs PCA).
- At the end of their hospital stay, we will document the following outcomes:
  - 1. Primary outcome: Length of stay (days)
  - 2. Secondary outcomes:
  - a. Number of hours the patient is NPO before diet is initiated
  - b. Mean pain scores on NRS over the first 24 hours, second 24 hours and course of their hospital stay
  - c. Total opioid dose for pain control during hospitalization (average MME during hospital stay)
  - d. Time to transition to PO opioids
  - e. Opioid-related adverse events/side effects: respiratory decompensation, sleep-disordered breathing, hypotension, nausea, vomiting, constipation, drowsiness, confusion, delirium or other mental status changes, myoclonus, headache, urinary retention, physician suspected opioid abuse or any form of allergic reaction.
  - f. Use of naloxone and antiemetics
  - g. Number of rescue doses required daily and in total through the hospital stay
  - h. ICU transfer
  - i. 30-day readmission rates
  - j. All-cause inpatient mortality and opioid-related inpatient mortality
  - k. 30-day mortality
  - I. Daily MME on discharge
- We expect to enroll patients over a 36-month period from the start date of the study. Based on this, we expect patient enrollment to end by 4/30/2024. We will plan to perform data analysis at two points: 1. Interim data analysis at a predetermined point in the study (mid-point of study), and 2. At the end of the study once patient enrollment has been completed.

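### Rescue-dose counts (secondary outcome g) are not comparable between arms at pain 7-10, because the same hydromorphone order is a base order in PDA and a rescue order in PCA

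*Combined protocol and SAP*

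**What the plan says.** Section B3.A lists as secondary outcome (g) the "Number of rescue doses required daily and in total through the hospital stay". It adds no definition of a rescue dose and does not say whether oral rescue counts. Section B3.B.b plans a t-test or Mann-Whitney U test for primary and secondary outcomes, at a 0.05 significance level.

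The two algorithms in B3.A set the orders:

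- **PDA, base orders:** "IV Hydromorphone 0.4 mg Q4H PRN for pain 4-6" and "IV hydromorphone 0.6 mg Q2H PRN for pain 7-10". Neither is labelled rescue.
- **PDA, rescue:** "Rescue IV hydromorphone 0.4 mg Q2H PRN for pain 4-10", to be given "if patient has persistent pain despite using Q4H PRN IV hydromorphone (breakthrough pain".
- **PCA, base order:** "IV Hydromorphone 0.1 mg Q10 minutes".
- **PCA, rescue:** 0.4 mg Q2H PRN for pain 4-6, and "hydromorphone 0.6 mg Q2H PRN for pain 7-10 = only to be given as a 'rescue' dose", for pain that persists despite the pump.

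Both arms have the same cap (1 mg per hour and 3 mg per 4 hours) and the same step-up rule: more than 2 rescue doses in 12 hours, or uncontrolled pain. The recommendations for all patients add an oral oxycodone rescue order. They also say that doses and frequencies are recommendations that may change.

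**The concern.** For pain 7-10, one order (same drug, route, dose, interval and pain band) is outside the rescue count in PDA and inside it in PCA. A patient therefore crosses a different threshold in each arm before a dose is counted. A p-value on (g) would invite the reading that one arm needed more extra analgesia, and the count cannot support that reading.

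The same count is one of the two conditions for step-up, so the labelling difference also enters a rule that is worded identically in both arms. The total count has a further weakness: it accumulates over the hospital stay, and length of stay is the primary outcome.

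**Working it through.** The plan gives no figure for (g), so there is nothing to reproduce. The 87 per group in B3.B.a concerns length of stay and is not an input here. The check sets the orders side by side and applies the protocol's own limits. It assumes that the cap covers all IV hydromorphone, pump plus rescue.

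**1. Labels by pain band**

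| Pain | Order outside the pump | PDA label | PCA label |
|---|---|---|---|
| 4-6 | 0.4 mg Q2H | rescue | rescue |
| 7-10 | 0.6 mg Q2H | base | rescue |
| 7-10 | 0.4 mg Q2H | rescue | not listed |

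The mismatch lies at pain 7-10. At pain 4-6 the rescue order is the same in both arms.

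**2. Effect of the label alone.** In 12 h there are 12 / 2 = 6 slots for a Q2H order. If k of them are filled with 0.6 mg for pain 7-10, the rescue count is 0 in PDA and k in PCA. At k = 3 the PCA count exceeds 2 and meets the rescue-count condition for step-up. The PDA count is still 0.

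**3. What the cap allows in PCA**

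- Full demand is 6 × 0.1 = 0.6 mg per hour, or 4 × 0.6 = 2.4 mg per 4 h. That leaves 3 − 2.4 = 0.6 mg, which is one 0.6 mg rescue per 4 h, or 3 per 12 h.
- In the rescue hour the 1 mg limit holds the pump to 1 − 0.6 = 0.4 mg. The 4 h total is then 0.4 + 0.6 + 3 × 0.6 = 2.8 mg, within 3 mg. So k = 3 is feasible close to full demand.
- For k = 6, rescue uses 2 × 0.6 = 1.2 mg per 4 h and leaves 3 − 1.2 = 1.8 mg for the pump. That is 1.8 / 2.4 = 75% of available demand. Six rescues fit only at or below that level of use.

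**4. What the cap allows in PDA.** The 0.6 mg Q2H order uses 2 × 0.6 = 1.2 mg per 4 h. Adding the 0.4 mg Q2H rescue gives 1.2 + 2 × 0.4 = 2.0 mg per 4 h, and at most 0.6 + 0.4 = 1.0 mg in any hour. Both are within the cap, so up to 6 rescues in 12 h are possible in PDA as well. This reads the PDA rescue order broadly. Its stated condition names only the Q4H order, which covers pain 4-6. Read literally, a patient treated only under the Q2H order has no stated route to a rescue dose.

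**5. Net direction.** Leaving aside the recommended step-up after the third rescue, either arm can record 0 to 6 rescues in 12 h. The difference, PCA minus PDA, can therefore lie anywhere from −6 to +6. The label raises the PCA count. The cap, continuous pump access and the broad PDA rescue order can lower it relative to PDA. With no rescue rates in the documents, neither sign nor size can be computed.

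**The case against.** The strongest reply is that rescue means the same thing in both arms: treatment of breakthrough pain beyond that arm's own base regimen. The count then measures failure of the assigned regimen, and a difference in base orders is what the trial compares. This stands as a reading of (g) within each arm, and it rules out the stronger inference that the outcome is biased by definition in a known direction. It does not rescue the between-arm test. The PDA base regimen already contains the dose that marks failure in PCA, and the plan never states this meaning for (g).

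A reader might also infer that identical treatment would be counted as 0 rescues in PDA and 6 in PCA, and that only the PCA patient would be stepped up. The documents do not support that as a typical contrast:

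- The PCA patient must also be using the pump, so total opioid is not identical, and six rescues fit the cap only with reduced pump use.
- Step-up is already recommended at the third rescue.
- Uncontrolled pain is a separate route to step-up in both arms, and a PDA patient who stays at pain 7-10 may well meet it.
- All doses and frequencies are recommendations.

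Nor do the documents say who gives the PRN doses. They assign nursing staff the pain scoring, so calling these nurse-given doses is an inference.

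Finally, (g) is counted daily as well as in total, which partly answers the dependence on length of stay, and opioid dose and NRS pain are already separate outcomes. Both points are fair, but neither gives a rescue dose a common meaning.

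**Conclusion.** The point holds as a lack of comparability, not as a demonstrated bias. At pain 7-10 an identical order is excluded from the count in PDA and included in PCA, so a between-arm test of (g) would mix labelling with need for analgesia. For three doses of 0.6 mg in 12 h, the label alone makes the difference between 0 and 3 counted rescues, and between missing and meeting the rescue-count condition for step-up. The net effect on trial results is unknown in size and sign.

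This rests on the recommended orders being broadly followed and on the cap covering pump and rescue doses together. It touches one of twelve secondary outcomes and one of two conditions for step-up. It does not affect the sample size or the primary test.

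**What to change.** Before analysis, the plan should:

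- State which orders count as rescue for (g), including whether the oral oxycodone rescue counts.
- Report (g) descriptively within each arm, as breakthrough treatment beyond that arm's own regimen, without a between-arm p-value.
- Base the between-arm comparison on total opioid MME in the first and second 24 h from randomisation, with every dose (pump, PRN, rescue, oral) counted the same way, read alongside NRS pain in the same windows. MME measures consumption, not breakthrough need, so neither should be read alone. Outcome (b) does not say when its first 24 h begins, so the plan should fix one starting point for both.

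Fixed windows are preferable to a rate per 24 h on IV opioids. Time on IV opioids is determined after randomisation, and time to oral transition is itself outcome (d).

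Separately, the sponsor should reconcile the rescue and step-up wording of the two algorithms, including the PDA rescue condition that names only the Q4H order. No dose change is proposed.

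The cost is analysis-plan wording. Outcome (c) already needs opioid doses; the fixed windows also need their times, so extra data collection should be small. The downside is that one planned secondary comparison becomes descriptive.

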#### B. Statistical Considerations

# a. Sample Size Justification:

- Data from a retrospective study of acute pancreatitis patients receiving either patient-controlled analgesia (PCA, n=116) or conventional IV push (IVP, n=647) showed that mean length of stay was higher in the PCA group (9.9 ± 7.14 days) compared to the IVP group (6.4 ± 9.86 days). The effect size calculated using this data yielded a Cohen's d=0.42. Therefore, assuming a 5% error probability for two groups, the estimated sample size to achieve 80% statistical power was determined to be 87 patients per group. At the midpoint of the study when half of target sample size is reached, preliminary post-hoc analysis will be performed to determine effect size and statistical power.

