# Recommended for all patients:

PO Acetaminophen 1000 mg Q8H scheduled

- IV Naloxone 40-80 mcg PRN for respiratory depression (RR<10) or significant somnolence
- PO Benadryl 25mg Q4H PRN moderate to severe pruritis
- Recommended algorithm for transition to oral:
- PO Oxycodone 5mg Q4H PRN for pain 4-6
- PO Oxycodone 10mg Q4H PRN for pain 7-10
- Rescue PO Oxycodone 5mg Q2H PRN for pain 4-10 = only to be given as a 'rescue dose' if patient has persistent pain despite using Q4H PO oxycodone (breakthrough pain)
- Dosing and frequencies of medications in the above algorithms are recommendations. The recommended doses are not required for maintenance in the study and we anticipate that they may change given patient characteristics and variable response to medication, the rapidly evolving nature of acute pancreatitis, and hospitalist preferences. However, the mode of IV opioid administration (PDA vs PCA) should remain as assigned until transition to PO opioid.
- Each patient will be closely monitored for adverse events related to opioid
  administration to include cardiorespiratory decompensation, hemodynamic
  instability, nausea, vomiting, confusion, altered mental status, headache,
  drowsiness, etc. This monitoring will include continuous pulse oximetry in addition to
  vital sign measurement every 4 hours.
- The efficacy of each treatment arm to adequately control the patient's pain will be assessed with scheduled use of the Numeric Rating Scale (NRS) every 4 hours by the nursing staff. Pain rating on the NRS will be documented by the nursing staff after each assessment. In an NRS, patients are asked to circle the number between 0 and 10 that fits best to their pain intensity. Zero usually represents 'no pain at all' whereas 10 represents 'the worst pain ever possible'.
- Likert scale of 1 to 10 (1 = Very poor, 10= excellent) will be used to grade overall patient satisfaction with pain control.
- Once each patient's pain is well controlled on IV opioid administration (as determined by the attending physician) and they can tolerate intake by mouth, transition from IV to PO opioid medication can be made in each arm by the attending physician. If the patient is unable to tolerate either the PDA or the PCA arm for any reason and requires switching over to the other arm as part of his/her clinical care, they will be withdrawn from the study and their data will be excluded while analyzing the results. AP has a variable course and may require IV opioids

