# b. Data Analysis:

- Primary and secondary outcomes of interest will be studied as outlined above. Data will be presented as mean ± standard deviation, median [interquartile range; range], and count (percentage), as appropriate. Data will be graphed, QQ plots performed and Shapiro-Wilk test utilized to assess for normality. Statistical tests for primary and secondary outcome will be compared using independent samples t-test and Mann-Whitney U test, as appropriate. Categorical variables were investigated using Pearson's Chi-Square. Statistical significance will be assigned at 0.05. All data will be analyzed using the R statistical software.

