# C. Subject Selection

We will study 174 patients admitted within 24 hours to the hospital with AP between 18 and 65 years of age. Patients will be randomized to receive IV opioids either via PCA (n=87) or PDA (n=87). Exclusion criteria are as follows: known allergy or contraindication to opioids, active illicit drug use, chronic pancreatitis, pancreatic cancer, acute encephalopathy/psychiatric illness that would preclude ability to use PCA, chronic renal insufficiency with a Cr >2, acute renal insufficiency with a Cr >3, and known allergy to acetaminophen or hepatic dysfunction otherwise limiting acteaminophen use.

Inclusion criteria	Exclusion criteria
Diagnosis of AP confirmed by revised Atlanta criteria	Active illicit drug use
	Discharged from the ED
Admitted to the medical floor within 48 hours of ED arrival	Direct admission to ICU from ED
	Known allergy to opioid medications
Age 18-65	Age <18 or >65
	Known chronic pain syndrome or concurrent medical condition with chronic pain
	Active
	encephalopathy/confusion/delirium/psychiatric

Study Description – Part B CCI Form: 9-2015 PI Revision Date: 3/2/2021

illness or any other condition that limits capacity
Known chronic opioid use
Renal insufficiency (baseline Creatinine of >2 and/or AKI with Cr>3 on admission)
Known allergy to acetaminophen or hepatic dysfunction otherwise limiting acetaminophen use

Subjects will be enrolled without regard to race, gender, or vulnerable category status.

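### The retrospective length-of-stay data give d of about 0.41, not 0.42, so 87 per group has about 76% power (two-sided t-test), not 80%; 80% needs 96 per group

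*Combined protocol and SAP*

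**What the plan says.** Length of stay is the primary outcome (section B3, Study Design). The Sample Size Justification bases its planning effect on a retrospective study of 116 PCA and 647 IV-push patients, in which "mean length of stay was higher in the PCA group (9.9 ± 7.14 days) compared to the IVP group (6.4 ± 9.86 days"). From this it concludes: "The effect size calculated using this data yielded a Cohen's d=0.42". With a 5% error probability, "the estimated sample size to achieve 80% statistical power was determined to be 87 patients per group". Subject Selection carries the number forward with equal allocation: "Patients will be randomized to receive IV opioids either via PCA (n=87) or PDA (n=87"), 174 in total.

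Under Data Analysis, outcomes "will be compared using independent samples t-test and Mann-Whitney U test, as appropriate", with significance at 0.05. The plan states neither the sidedness of the test nor the SD convention behind d. It makes no allowance for losses, although patients who need to change arms are handled as follows: "they will be withdrawn from the study and their data will be excluded while analyzing the results". At the midpoint, "preliminary post-hoc analysis will be performed to determine effect size and statistical power", but no rule for changing the sample size is given.

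**The concern.** The justification prints every input needed to recompute d, and the recomputed value is smaller than the one stated. The step from d = 0.42 to 87 per group also falls slightly short. Both departures favour the plan.

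What is at stake is the power claim for the primary outcome. If 87 per group does not give 80% power for the 3.5-day planning difference, the chance of missing such a difference is higher than the plan says, and a non-significant t-test would be credited with more power than the quoted data support.

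**Working it through.** **Inputs.** Means 9.9 and 6.4 days, SDs 7.14 and 9.86 days, retrospective group sizes 116 and 647, alpha 0.05, power 80%, 87 per group (all from Sample Size Justification); 1:1 allocation (Subject Selection); independent-samples t-test (Data Analysis). Two-sided testing is assumed.

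**1. The plan's own figure, starting from d = 0.42.**
- Normal formula: n = 2(1.960 + 0.842)²/0.42² = 88.99, so 89 per group.
- Noncentral t: 89.96, so 90 per group.
- Power at 87 per group: 79.1% (normal) or 78.7% (t).
- One-sided 0.05: 71 per group.

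So 87 is close to the two-sided answer for d = 0.42, a little low, and far from the one-sided answer.

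**2. d from the printed data.**
- Difference = 9.9 − 6.4 = 3.5 days.
- Equal-weight SD = √((7.14² + 9.86²)/2) = √((50.98 + 97.22)/2) = 8.608 days.
- d = 3.5/8.608 = 0.4066.

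This is the right SD for a 1:1 trial, because the standard error of the difference depends on exactly this quantity. A d of 0.42 would need an SD of 3.5/0.42 = 8.33 days.

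Other conventions, with two-sided t-test results where they bear on the point:

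| SD used | d | Power at 87 | n per group for 80% |
|---|---|---|---|
| Equal-weight | 0.407 | 76.0% | 96 |
| Arithmetic mean of the two SDs | 0.412 | 77.1% | 94 |
| Pooled, weighted by 116 and 647 (9.50 days) | 0.368 | 67.6% | 117 |
| IV-push SD alone | 0.355 | 64.4% | 126 |
| PCA SD alone | 0.490 | 89.5% | 67 |

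None gives 0.42. The weighted pooled SD reflects the retrospective 116:647 split and is shown for reference only.

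**3. Power at 87 per group.**
- SE of the difference = √(7.14²/87 + 9.86²/87) = 1.305 days.
- Noncentrality = 3.5/1.305 = 2.682, df = 172.
- Two-sided 0.05 power = 76.0%. A Welch calculation with the two SDs also gives 76.0%, as does a simulation of 100,000 trials with normal data.

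**4. Sample size for 80% power.** n = 95.92, so 96 per group, 192 in total (power 79.6% at 95 and 80.0% at 96).

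**5. Where the 4.0 missing points arise.** From d: 78.7% − 76.0%, which is 2.6 points before rounding. From the step to 87: 80.0% − 78.7% = 1.3 points.

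**6. Rounding of the printed means.** Each mean is given to one decimal, so the difference lies between 3.4 and 3.6 days.
- 3.4 days: d = 0.395, power 73.6%, 102 per group.
- 3.6 days: d = 0.418, power 78.3%, 91 per group.
- d rounds to 0.42 only if the difference is at least 0.415 × 8.608 = 3.57 days.

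**7. Difference that 87 per group detects with 80% power.** d = 0.427, and 0.427 × 8.608 = 3.68 days, about 3.7.

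**8. One-sided 0.05 at d = 0.4066.** n = 75.5, so 76 per group, which does not explain 87.

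**The case against.** The strongest reply has four parts.

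- **Rounding.** If both means sit near the edges of their rounding intervals, the difference could reach 3.57 days or more and d would print as 0.42. This is unlikely but not excluded. It could rescue the stated d, but not the stated power, which would still be at most 78.3%.
- **The second step.** A printed 0.42 could be as high as almost 0.425, where the normal formula gives 86.9, so 87. The 1.3 points charged to the step from d to 87 may therefore be rounding of d plus choice of formula. That stands: as printed the step falls short, but it is small and the main discrepancy is in deriving d from the data.
- **Unstated conventions.** The plan names neither SD convention nor sidedness, so 76% rests on an equal-weight SD and a two-sided test. True, but the weighted pooled SD makes matters worse, and a one-sided test does not reproduce 87.
- **Materiality.** The change in d is 0.013, while d from 116 and 647 patients has a standard error of about √(1/116 + 1/647 + 0.407²/1526) = 0.10. The IV-push SD exceeds its mean, which points to skewed stays and possibly a Mann-Whitney test. The remedy also changes no analysis. These points limit the weight of the finding. They do not make 80% the correct figure for the stated inputs, and the calculation above makes no claim about Mann-Whitney power.

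**Conclusion.** The concern holds. On the plan's own printed data, d is about 0.41, power at 87 per group is 76.0% rather than 80%, and 80% power needs 96 per group (91 to 102 over rounding of the means). The chance of missing a true 3.5-day difference is about 24%, not 20%, and the difference detectable with 80% power, 3.7 days, lies above the planning difference.

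The result assumes a two-sided 0.05 t-test, the equal-weight SD that suits 1:1 allocation, and 87 analysed patients in each arm. The last is a best case, since patients who switch arms are to be excluded and no allowance is made for them. The midpoint look does not repair the statement, because no rule links it to the sample size. The error is modest but should be corrected, since it concerns the only power statement for the primary outcome.

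**What to change.** Keep 174 patients and replace the effect-size and power statements in the Sample Size Justification with text to this effect:

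> The retrospective data give d = 0.41 (difference 3.5 days, equal-weight SD 8.61 days). For a two-sided 0.05 t-test, 87 per group gives about 76% power for this difference, and 80% power for d = 0.43, about 3.7 days. These figures are for the t-test and are before any loss from excluding patients who switch arms.

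This names the SD convention and the sidedness, so a reader can reproduce the figures. It needs no extra patients and no change to the analysis. The only cost is a slightly less favourable stated power. If the sponsor wants to keep the 80% claim for 3.5 days, the target would have to rise to 96 per group, 18 more patients in total (192 − 174).
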